#### **8.6.1.2. Sensitivity Analyses**

The above primary efficacy analysis will be repeated using the PP population. Sensitivity analyses are considered supportive.

To assess the robustness of the primary efficacy result, the following sensitivity analyses will be conducted using the ITT population:

- a. The same imputation method above will be repeated based on the Pattern-Mixture Model as discussed by Ratitch et al. under the Missing Not at Random (MNAR) assumption, by using the profiles from placebo patients with observed data to impute missing data.
- b. Patients who withdraw early, before the confirmation of their target wound closing or their 3-month visit (without target wound closure), will be considered treatment failures with respect to the second primary endpoint.

The treatment-by-covariate interaction will be tested in a separate model for each endpoint and each covariate. Sensitivity analyses will not be done for subgroups.

#### **8.6.2. Analysis of Key Secondary Efficacy Endpoints**

Formal statistical testing of the secondary efficacy endpoints will be performed after the two primary efficacy endpoints achieve statistical significance. To control overall Type I error rate at 5%, the step-down strategy will be applied as described in Section 7.5.

The covariates ie., EB type and Baseline characteristics (of the secondary endpoint being analyzed), will be used for the secondary analyses as they are for the primary analyses. Target wound age and target wound size will be used for:

- Proportion of patients experiencing complete closure of their target wound within 2 months

- Proportion of patients experiencing complete closure of their target wound within 1 month.

For other secondary endpoints, target wound age and target wound size will not be used as covariates because they are not considered effect modifiers.

**Table 3: Analysis Strategy for Efficacy Endpoints**

Endpoint	Primary vs. Supportive Approach	Statistical Method	Analysis Population	Missing Data Approach
Two primary endpoints				
Time to complete target wound closure within 3 months	P	Cox Model	ITT	Censoring
	S	Log-rank Test	ITT	Censoring
	S	Cox Model	PP	Censoring
	S	Log-rank Test	PP	Censoring
	S	Descriptive Statistics	ITT	As observed
Complete closure of target wound within 3 months	P	Logistic Regression	ITT	MI
	S	Logistic Regression	PP	MI
	S	Logistic Regression	ITT	MI (MNAR)
	S	Logistic Regression	ITT	Missing as Failures
	S	Descriptive Statistics	ITT	As observed
Key Secondary Endpoints				
Complete closure of target wound within 2 months	P	Logistic Regression	ITT	MI
	S	Descriptive Statistics	ITT	As observed
Complete closure of target wound within 1 month	P	Logistic Regression	ITT	MI
	S	Descriptive Statistics	ITT	As observed

**Table 3: Analysis Strategy for Efficacy Endpoints (Continued)**

Endpoint	Primary vs. Supportive Approach	Statistical Method	Analysis Population	Missing Data Approach
Change in BSAI of lesional skin at Month 3, compared to Baseline	P	MMRM	ITT	MI
	S	MMRM	ITT	As observed
	S	ANCOVA	ITT	MI As observed
	S	ANCOVA on transformed data	ITT	MI As observed
	S	Descriptive Statistics	ITT	As observed
Change in BSAI of Total Body Wound Burden at Month 3, compared to Baseline	P	MMRM	ITT	MI
	S	MMRM	ITT	As observed
	S	ANCOVA	ITT	MI As observed
	S	ANCOVA on transformed data	ITT	MI As observed
	S	Descriptive Statistics	ITT	As observed
Change in Itching assessment at Day 7, compared to Baseline	P	Logistic Regression	ITT	As observed
	S	Logistic Regression	ITT	As observed excluding missing
	S	Descriptive Statistics	ITT	As observed
Change in Pain assessment at Day 7, compared to Baseline	P	Logistic Regression	ITT	As observed
	S	Logistic Regression	ITT	As observed excluding missing
	S	Descriptive Statistics	ITT	As observed

**Table 3: Analysis Strategy for Efficacy Endpoints (Continued)**

Endpoint	Primary vs. Supportive Approach	Statistical Method	Analysis Population	Missing Data Approach
Other Secondary Endpoints				
Change in BSAI of Total Body Wound Burden at Weeks 2, Months 1 and 2, compared to Baseline	P	MMRM	ITT	MI
	S	MMRM	ITT	As observed
	S	ANCOVA	ITT	MI As observed
	S	ANCOVA on transformed data	ITT	MI As observed
	S	Descriptive Statistics	ITT	As observed
Percent change from Baseline in BSAI of Total Body Wound Burden at Week 2 Months 1, 2, and 3	P	MMRM	ITT	MI
	S	MMRM	ITT	As observed
	S	ANCOVA	ITT	MI As observed
	S	ANCOVA on transformed data	ITT	MI As observed
	S	Descriptive Statistics	ITT	As observed
Percent change in BSAI of lesional skin at Week 2, Months 1, 2, and 3, compared to Baseline	P	MMRM	ITT	MI
	S	MMRM	ITT	As observed
	S	ANCOVA	ITT	MI As observed
	S	ANCOVA on transformed data	ITT	MI As observed
	S	Descriptive Statistics	ITT	As observed

**Table 3: Analysis Strategy for Efficacy Endpoints (Continued)**

Endpoint	Primary vs. Supportive Approach	Statistical Method	Analysis Population	Missing Data Approach
Change in BSAI of lesional skin at Week 2, Month 1 and Month 2, compared to Baseline	P	MMRM	ITT	MI
	S	MMRM	ITT	As observed
	S	ANCOVA	ITT	MI As observed
	S	ANCOVA on transformed data	ITT	MI As observed
	S	Descriptive Statistics	ITT	As observed
Presence of scarring of healed target wound at the visit where the complete closure is documented	P	Descriptive Statistics	ITT with wound closure	As observed
Change in target wound characteristics (ie. milia, inflammation, blistering, granulation tissue, erythema, exudate) at Week 2, Months 1, 2, and 3, compared to Baseline	P	Logistic regression	ITT	As observed
	S	Descriptive Statistics	ITT	As observed
Change in Itching and Pain at Days 1 to 6, Week 2, and Months 1, 2 and, 3, compared to Baseline	P	Logistic Regression	ITT	As observed
	S	Logistic Regression	ITT	As observed (excluding missing)
	S	Descriptive Statistics	ITT	As observed
Target Wound Closure within Week 2, compared to Baseline	P	Logistic Regression	ITT	MI
	S	Descriptive Statistics	ITT	As observed

Abbreviations: MMRM=Mixed model for repeated measures with treatment, visit, and visit-treatment interaction as fixed effects; P=Primary approach; S=Supportive approach

The analysis of key secondary efficacy variables will be as follows:

- Proportion of patients experiencing complete target wound closure at Month 2  
 This assessment will be analyzed using the same approach as the second primary endpoint.
- Proportion of patients experiencing complete target wound closure at Month 1

This assessment will be analyzed using the same approach as the second primary endpoint.

- Change in lesional skin based on BSAI at Month 3 compared to Baseline

For analysis, a mixed model repeated measures approach (using Restricted Maximum Likelihood (REML) estimation) will be used on each multiply imputed data set. The model will include treatment, Baseline BSAI, EB type, visit, and visit-treatment interaction as the fixed effects. Visit will be used as a repeated measure and an unstructured covariance approach will be applied. If the fit of the unstructured covariance structure fails to converge, the following covariance structures will be tried in order until convergence is reached: Toeplitz with heterogeneity, autoregressive with heterogeneity, Toeplitz, and autoregressive.

Means and least squares mean difference between SD-101-6% and Placebo, along with a two-sided 95% CI and p-value for the difference between treatments will also be provided.

The following provides sample code for implementing the MMRM analysis:

```
proc mixed method = reml;  
    class TRT VISIT SUBJID;  
    model <CHG>=TRT VISIT TRT*VISIT BASELINE  
    EBTYPE/s ddfm=kr;  
    repeated VISIT/type=UN subject=SUBJID;  
    lsmeans TRT*VISIT /slice=VISIT pdiff diff alpha=0.05 cl;  
    /*testing difference in treatment group level for each visit*/;  
run;
```

where TRT is the assigned treatment, VISIT is the visit based on the window mapping, CHG is the change from Baseline in the BSAI measurements, EBTYPE is the EB type, and BASELINE is the Baseline BSAI measurements.

In addition, the difference in changes will be presented across each of the subgroups (see Section 7.6) using descriptive statistics. MMRM with a subgroup factor in the model will be applied. In case the effects are not estimable, a simple ANCOVA analysis of covariance) model with EB type and Baseline BSAI measurement as covariates will be used with treatment and subgroup as fixed effect in the model.

As decided post database lock, for target wound age, the following categorization will be used:  $0 \leq 30$  days,  $>30$  days.

As clarified in the NTF, if any of covariates are missing, then a subject with a missing covariate will be excluded from the ANCOVA model.

The above analyses will be conducted on the data after MI imputation. Analysis on the observed data will be conducted as a sensitivity analysis.

A graph of the mean BSAI of lesional skin for each treatment group over time will also be presented.

- Change in Total Body Wound Burden at Month 3, compared to Baseline

It is anticipated that no patients will withdraw from the study prior to Day 7. To provide an analysis of the sensitivity of the conclusions resulting from the analysis of pain at Day 7, an additional analysis will be performed on the ITT population, but will not consider missing pain scores and will only compare the proportions of patients categorized as Improved or Not Improved.

Descriptive statistics will be presented for two categories defined above and for the actual scores at Baseline and Day 7, as well as the change in pain scores from Baseline to Day 7.

The treatment-by-covariate interaction will be tested in a separate model for each endpoint and each covariate. Subgroup means and 95% CI's will be presented as derived from this model. The plot of individual patient values on y-axis and covariate on x-axis, using different symbols for each treatment and a regression line for each treatment will be presented for continuous data.

In addition, same analysis as above will be conducted for subgroup factors listed in Section 7.6 keeping continuous factors as continuous (eg. patient's age).

In addition, the consistency of the treatment effect across each of the subgroups (see Section 7.6) will be evaluated using descriptive statistics.

For continuous secondary endpoints, normality will be assessed via Shapiro-Wilk test statistics' values and graphically. If suggestion of substantial departure from normality is detected, then the data will be transformed using log or rank transformations to yield analysis scale closest to normality. ANCOVA with EB type and Baseline value for the endpoint under analysis will be performed on transformed values.

Supportive analyses (Table 3) will not be done for subgroups.

### **8.6.3. Analyses of Other Secondary Endpoints**

The analysis of other secondary efficacy endpoints will be as follows:

- Change in Total Body Wound Burden at Week 2, Months 1, and 2, compared to Baseline.
- Percent change from Baseline in Total Body Wound Burden at Week 2, Months 1, 2, and 3.
- Percent change in lesional skin based on BSAI at Week 2, Months 1, 2, and 3, compared to Baseline
- Change in lesional skin based on BSAI at Week 2, and Months 1 and 2, compared to Baseline.
- The four endpoints listed above will be analyzed using the same approach as the change at Month 3 for both change from Baseline and the percentage change from Baseline. Although the comparison of Month 3 against Baseline is a key secondary endpoint, these other time points will be included in the exploration of a temporal pattern. Presence of scarring of healed target wound at visit of documented complete wound closure.

The proportion of patients experiencing scarring will be presented for each of the two treatment groups only for those patients who experienced complete closure of target wound.

- Change in target wound characteristics (ie. milia, inflammation, blistering, granulation tissue, erythema, exudate) at Week 2, Months 1, 2, and 3, compared to Baseline.

As clarified in the NTF, the presence of each characteristic was recorded as Yes on the CRF. The blank value will be considered the absence of a characteristics. The same approach used in the evaluation of itching and pain as key secondary endpoints

on observed data will be employed in the analysis of these endpoints, but will be performed at each of the specified visits. The categorization will be as follows:

Baseline	Post-baseline	Category
Absent	Absent	Improved or Absent
Present	Absent	Improved or Absent
Absent	Present	Not Improved
Present	Present	Not Improved

Assessments will be summarized using descriptive statistics at each visit by treatment group. A plot comparing the two treatments over time will also be presented for each endpoint.

- Change in itching and pain at Days 1 to 6, Week 2, and Months 1, 2, and 3, compared to Baseline.

The same approaches used in the evaluation of itching and pain as key secondary endpoints will be employed in the analysis of these endpoints, but will be performed at each of the specified visits. Assessments will be summarized using descriptive statistics at each visit by treatment group. A plot comparing the two treatments over time will also be presented for each endpoint.

- Proportion of patients experiencing target wound closure within Week 2.

This assessment will be analyzed independently at each visit using the same approach as the Month 3 primary endpoint.

Supportive analyses will not be done for subgroups.

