9.3. Other Secondary Efficacy Endpoints

- Change in Total Body Wound Burden based on BSAI at Week 2 and Months 1 and 2, compared to Baseline
- Percent change from Baseline in Total Body Wound Burden based on BSAI at Week 2 and Months 1, 2, and 3
- Change in lesional skin based on BSAI at Week 2 and Months 1 and 2, compared to Baseline
- Percent change in lesional skin based on BSAI at Week 2 and Months 1, 2, and 3, compared to Baseline
- Presence of scarring of healed target wound at the visit where the complete closure is documented
- Change in target wound characteristics (ie, inflammation, blistering, granulation tissue, erythema, exudate) at Week 2 and Months 1, 2, and 3, compared to Baseline
- Change in itching and pain at Days 1 to 6, Week 2, and Months 1, 2, and 3, compared to Baseline
- Proportion of patients experiencing target wound closure within Week 2

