17. APPENDICES

17.1. Appendix 1: EB Subtypes

Clinical Features of EB

Epidermolysis Bullosa Simplex (EBS)

EBS Subtypes	Features
Weber-Cockayne	
• Most common and localized form of EBS.• Blisters develop on hands and feet in response to friction.• Usually presents in infancy as child is starting to crawl and walk.• Lesions heal without scarring but there may be thickening of the skin on soles and palms.
Koebner	
• Generalized EBS where blisters develop all over the body but commonly on hands, feet and extremities.• Presents at birth or early in infancy.• May be mild involvement of mucous membranes and nails.• Thickening of skin and plaques develop on palms and soles.
Dowling-Meara	
• Generalized and severe form of EBS.• Presents at birth with blistering on the face, trunk and limbs.• Thickened skin may cause calluses that limit or interfere with joint movement.• Nails often affected.• May involve other organs including inside the mouth, gastrointestinal and respiratory tract.• Widespread involvement may cause death in infancy but usually there is significant improvement with age.
EB with muscular dystrophy	
• Due to plectin mutation.• Variable degree of blistering followed later in life by muscular dystrophy.• Muscular dystrophy does not arise in all cases with plectin mutation.

Recessive Dystrophic Epidermolysis Bullosa (RDEB)

[figure not shown]
DEB Subtypes	Features
Recessive DEB	
• May present with severe blistering (Hallopeau-Siemens) or mild disease (non-Hallopeau-Siemens).• Generalized severe blistering is more common and involves large areas of skin and mucous membranes.• Blisters heal but with scarring and deformity causing limited movement as fingers and toes may be fused together (mitten hands).• Complications such as infection, malnutrition and dehydration may cause death in infancy and those that survive are at great risk of developing squamous cell carcinoma.• Milia (small white cysts) are often present at healed but scarred sites.

Junctional Epidermolysis Bullosa (JEB)

JEB Subtypes	Features

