### **6.3.3. Other Secondary Efficacy Endpoints**

The additional efficacy endpoints are:

- Change in Total Body Wound Burden based on BSAI at Week 2, Months 1, and 2, compared to Baseline.
- Percent change from Baseline in Total Body Wound Burden based on BSAI at 2 Week 2 weeks, Months 1, 2, and 3.
- Change in lesional skin based on BSAI at Week 2, Months 1, and 2, compared to Baseline.
- Percent change in lesional skin based on BSAI at Week 2, Months 1, 2, and 3, compared to Baseline.
- Presence of scarring of healed target wound at the visit where the complete closure is documented.
- Change in target wound characteristics (ie.: inflammation, blistering, granulation tissue, erythema, exudate) at Week 2, Months 1, 2, and 3, compared to Baseline.
- Changes in itching and pain at Days 1 to 6, Week 2, and Months 1, 2, and 3 compared to Baseline.
- Proportion of patients experiencing target wound closure within Week 2.

The analysis will be performed on the ITT population and subgroups of interest.

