Ad-hoc Table 14.2.15.2.1.7	Summary of Change in Target Wound Blistering by Visit (Age 2 Years to <12 Years and Baseline BSAI of Total Body Wound Burden $\geq 5\%$ ) (ITT Population)
Table 14.2.15.2.2	Logistic Regression for Change in Target Wound Blistering by Visit (ITT Population)
Ad-hoc Table 14.2.15.2.2.2	Logistic Regression for Change in Target Wound Blistering by Visit (Age 2 Years to <12 Years) (ITT Population)
Ad-hoc Table 14.2.15.2.2.3	Logistic Regression for Change in Target Wound Blistering by Visit (Baseline Target Wound Age >30 Days) (ITT Population)
Ad-hoc Table 14.2.15.2.2.4	Logistic Regression for Change in Target Wound Blistering by Visit (Recessive Dystrophic EB Type) (ITT Population)
Ad-hoc Table 14.2.15.2.2.5	Logistic Regression for Change in Target Wound Blistering by Visit (Baseline BSAI of Total Body Wound Burden $\geq 5\%$ ) (ITT Population)
Ad-hoc Table 14.2.15.2.2.6	Logistic Regression for Change in Target Wound Blistering by Visit (Age 2 Years to <12 Years and Recessive Dystrophic EB Type) (ITT Population)
Ad-hoc Table 14.2.15.2.2.7	Logistic Regression for Change in Target Wound Blistering by Visit (Age 2 Years to <12 Years and Baseline BSAI of Total Body Wound Burden $\geq 5\%$ ) (ITT Population)
Table 14.2.15.3.1	Summary of Change in Target Wound Milia by Visit (ITT Population)
Ad-hoc Table 14.2.15.3.1.2	Summary of Change in Target Wound Milia by Visit (Age 2 Years to <12 Years) (ITT Population)
Ad-hoc Table 14.2.15.3.1.3	Summary of Change in Target Wound Milia by Visit (Baseline Target Wound Age >30 Days) (ITT Population)
Ad-hoc Table 14.2.15.3.1.4	Summary of Change in Target Wound Milia by Visit (Recessive Dystrophic EB Type) (ITT Population)
Ad-hoc Table 14.2.15.3.1.5	Summary of Change in Target Wound Milia by Visit (Baseline BSAI of Total Body Wound Burden $\geq 5\%$ ) (ITT Population)

Table Number	Table Title
Ad-hoc Table 14.2.15.3.1.6	Summary of Change in Target Wound Milia by Visit (Age 2 Years to <12 Years and Recessive Dystrophic EB Type) (ITT Population)
Ad-hoc Table 14.2.15.3.1.7	Summary of Change in Target Wound Milia by Visit (Age 2 Years to <12 Years and Baseline BSAI of Total Body Wound Burden $\geq 5\%$ ) (ITT Population)
Table 14.2.15.3.2	Logistic Regression for Change in Target Wound Milia by Visit (ITT Population)
Ad-hoc Table 14.2.15.3.2.2	Logistic Regression for Change in Target Wound Milia by Visit (Age 2 Years to <12 Years) (ITT Population)

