Ad-hoc Table 14.2.15.3.2.3	Logistic Regression for Change in Target Wound Milia by Visit (Baseline Target Wound Age >30 Days) (ITT Population)
Ad-hoc Table 14.2.15.3.2.4	Logistic Regression for Change in Target Wound Milia by Visit (Recessive Dystrophic EB Type) (ITT Population)
Ad-hoc Table 14.2.15.3.2.5	Logistic Regression for Change in Target Wound Milia by Visit (Baseline BSAI of Total Body Wound Burden $\geq 5\%$ ) (ITT Population)
Ad-hoc Table 14.2.15.3.2.6	Logistic Regression for Change in Target Wound Milia by Visit (Age 2 Years to <12 Years and Recessive Dystrophic EB Type) (ITT Population)
Ad-hoc Table 14.2.15.3.2.7	Logistic Regression for Change in Target Wound Milia by Visit (Age 2 Years to <12 Year and Baseline BSAI of Total Body Wound Burden $\geq 5\%$ ) (ITT Population)
Table 14.2.15.4.1	Summary of Change in Target Wound Erythema by Visit (ITT Population)
Ad-hoc Table 14.2.15.4.1.2	Summary of Change in Target Wound Erythema by Visit (Age 2 Years to <12 Years) (ITT Population)
Ad-hoc Table 14.2.15.4.1.3	Summary of Change in Target Wound Erythema by Visit (Baseline Target Wound Age >30 Days) (ITT Population)
Ad-hoc Table 14.2.15.4.1.4	Summary of Change in Target Wound Erythema by Visit (Recessive Dystrophic EB Type) (ITT Population)
Ad-hoc Table 14.2.15.4.1.5	Summary of Change in Target Wound Erythema by Visit (Baseline BSAI of Total Body Wound Burden $\geq 5\%$ ) (ITT Population)
Ad-hoc Table 14.2.15.4.1.6	Summary of Change in Target Wound Erythema by Visit (Age 2 Years to <12 Years and Recessive Dystrophic EB Type) (ITT Population)
Ad-hoc Table 14.2.15.4.1.7	Summary of Change in Target Wound Erythema by Visit (Age 2 Years to <12 Years and Baseline BSAI of Total Body Wound Burden $\geq 5\%$ ) (ITT Population)
Table 14.2.15.4.2	Logistic Regression for Change in Target Wound Erythema by Visit (ITT Population)
Ad-hoc Table 14.2.15.4.2.2	Logistic Regression for Change in Target Wound Erythema by Visit (Age 2 Years to <12 Years) (ITT Population)

Table Number	Table Title
Ad-hoc Table 14.2.15.4.2.3	Logistic Regression for Change in Target Wound Erythema by Visit (Baseline Target Wound Age >30 Days) (ITT Population)
Ad-hoc Table 14.2.15.4.2.4	Logistic Regression for Change in Target Wound Erythema by Visit (Recessive Dystrophic EB Type) (ITT Population)
Ad-hoc Table 14.2.15.4.2.5	Logistic Regression for Change in Target Wound Erythema by Visit (Baseline BSAI of Total Body Wound Burden >=5%) (ITT Population)

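### SAP 8.6.3 scores milia at the target wound as 'Not Improved' in all ITT patients, so the milia odds ratio partly reflects wound closure, in a direction that depends on how milia were recorded

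*SAP*

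**What the plan says.** SAP 8.6.3 lists the signs as "Change in target wound characteristics (ie. milia, inflammation, blistering, granulation tissue, erythema, exudate". One four-row table codes them all. Absence at the visit is 'Improved or Absent' and presence is 'Not Improved', whatever the baseline state. The CRF recorded presence only, and the SAP adds: "The blank value will be considered the absence of a characteristics".

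Table 3 assigns logistic regression in the ITT population on observed data, at Week 2 and Months 1, 2 and 3. List 11.3 carries this out for milia in Table 14.2.15.3.2, "Logistic Regression for Change in Target Wound Milia by Visit (ITT Population", and again in Ad-hoc Table 14.2.15.3.2.4 for recessive dystrophic EB, "Logistic Regression for Change in Target Wound Milia by Visit (Recessive Dystrophic EB Type) (ITT Population". Neither title carries a condition on closure.

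Two other places bear on this. Protocol Appendix 1, under recessive dystrophic EB, says: "Milia (small white cysts) are often present at healed but scarred sites". And SAP 8.6.3 reports scarring "only for those patients who experienced complete closure of target wound".

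Milia are in neither endpoint list. Protocol 9.3 has "Change in target wound characteristics (ie, inflammation, blistering, granulation tissue, erythema, exudate) at Week 2" and SAP 6.3.3 has "Change in target wound characteristics (ie.: inflammation, blistering, granulation tissue, erythema, exudate) at Week 2". Both name granulation tissue, yet Tables 14.2.15.1 to 14.2.15.5 cover inflammation, blistering, milia, erythema and exudate only. SAP 5.2 does not record that granulation tissue was dropped.

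**The concern.** The rule suits signs that mark an active wound, such as inflammation, blistering, erythema and exudate. Milia differ, because the protocol associates them with skin that has healed. Under the rule, a wound that stays open without milia scores as a success, and a wound that closes and then shows milia scores as a failure. Closure comes after randomisation and is what the treatment is meant to change, so the model's baseline covariates cannot remove its influence.

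What is at stake is interpretation. A milia odds ratio below 1 could be read as the cream worsening the wound when the arms differ only in how many wounds healed. A real reduction of milia on healed skin could also be hidden. The recessive dystrophic EB table is the most exposed, because the protocol's statement concerns that type.

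**Working it through.** **Inputs.** From SAP 4.4: closure by Month 3 of 60% on SD-101-6% and 35% on placebo, 75 patients per arm, exponential hazards. The stated hazard ratio reproduces: ln(0.40)/ln(0.65) = 2.127. The documents give no milia rates and no EB-type mix, so those below are assumptions.

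**Formulas.** With closure rate c, milia on a share h of closed wounds and o of open wounds, equal in both arms:

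- P('Not Improved') = c × h + (1 − c) × o
- Active minus placebo = (0.60 − 0.35) × (h − o) = 0.25 × (h − o)
- Odds ratio (OR) for 'Improved or Absent' = [(1 − pA)/pA] / [(1 − pP)/pP]

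The sign of the difference depends only on whether h exceeds o.

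**Month 3, milia on closed wounds only (o = 0).** The chance is that of nominal two-sided p < 0.05 against the cream (exact binomial enumeration, unadjusted Pearson chi-square, 75 per arm).

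| h | Active | Placebo | OR | Chance |
|---|---|---|---|---|
| 10% | 6.0% | 3.5% | 0.57 | 10% |
| 20% | 12.0% | 7.0% | 0.55 | 18% |
| 40% | 24.0% | 14.0% | 0.52 | 35% |

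Among closed wounds the OR is 1.00 in every row.

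**A real benefit.** If the cream halved milia on healed skin (20% v 40%), the OR among closed wounds is (0.80/0.20)/(0.60/0.40) = 2.67. The planned analysis would expect 0.60 × 0.20 = 12% v 0.35 × 0.40 = 14%, OR 1.19. The planned OR reaches 1 only when the milia rate on healed skin falls to 0.35/0.60 = 0.583 of the placebo rate, a 42% cut.

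**Earlier visits.** Under exponential hazards, closure by day d is 1 − 0.40^(d/90) v 1 − 0.65^(d/90): about 13% v 6% at Day 14 and 26% v 13% at Day 30. With h = 10% and o = 0, 'Not Improved' is 1.3% v 0.6% and 2.6% v 1.3%, and the chance is about 1% and 5%. The OR is no closer to 1, but so few patients are affected that a nominal result is less likely.

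**Other EB types.** If only half the patients can form milia, h = 40% gives 12% v 7%, with a chance of 18% instead of 35%.

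**Milia unrelated to closure.** If an independent 10% of patients also have milia whatever the wound status, P = 1 − 0.90 × (1 − c × h). For h = 10% this is 15.4% v 13.2%, OR 0.83; for h = 40%, 31.6% v 22.6%, OR 0.63.

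**No distortion, or the reverse.**

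- Equally common (h = o = 20%): 20% v 20%, OR 1.00.
- Commoner on open wounds (h = 10%, o = 20%): 14.0% v 16.5%, OR 1.21 in favour of the cream.
- Left blank after closure and so read as absent, with o = 10%: 0.40 × 0.10 = 4.0% v 0.65 × 0.10 = 6.5%, OR 1.67 in favour of the cream.

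**The case against.** The strongest objection is that the mechanism needs milia to be recorded on wounds that have closed, and the documents do not say they were. In Protocol Section 11, the one item specific to a healed target wound is scarring. If the other signs were left blank once a wound closed, the distortion runs the other way. This stands. A reader might infer from Appendix 1 that the rule is biased against the cream, and the documents do not support that as a fixed direction.

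The clinical support is also thin. It is one line, for recessive dystrophic EB only, with no rate, no time to onset within 90 days and nothing on milia around open wounds. This stands too, and is why the size is given as a range that includes zero and reversal. The 60% v 35% figures apply to Month 3 alone. SAP 6.3.1 treats a wound once closed as closed thereafter, so they need not describe the skin at that visit. Because the analysis uses observed data, 75 per arm is an upper limit.

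Finally, presence of a sign in all randomised patients is a comparison that respects randomisation, while restricting to closed wounds does not. Descriptive milia tables, scarring tables and patient listings are already planned. That is a reason to keep the planned table, but not to leave it unexplained: the 'Not Improved' label invites a reading in terms of wound worsening that this sign does not bear. The SAP itself uses the closed-wound denominator for scarring.

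**Conclusion.** The point holds in conditional form. The coding, the unrestricted ITT population and the protocol's statement on milia are all on the page, and together they make the milia odds ratio partly a measure of closure. At Month 3 the expected OR is 0.57 to 0.52 when closed wounds carry milia at 10% to 40%, open wounds carry none, and signs are recorded after closure. It is nearer 1 with a background of milia, exactly 1 if closed and open wounds carry milia equally often, and above 1 if milia are commoner on open wounds or if blanks after closure hide those on healed skin.

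Two further inferences should not be drawn. The trial's conclusions are not at risk: SAP 7.5 treats these tests as exploratory, outside the step-down sequence. Nor is a matching bias shown for granulation tissue. Protocol 5.1 names its stimulation among allantoin's reported effects, but no direction or size has been worked out. What is established there is narrower: a listed endpoint has no table of its own in list 11.3, although Figure 14.2.15.1 and Listing 16.2.15 may show it.

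**What to change.** 1. Check Listing 16.2.15 to see whether signs were recorded at and after closure. This settles which direction of distortion is possible.
2. In SAP 8.6.3, add a descriptive table of milia by arm among patients with complete closure, at the visit where closure is documented, with the number closed as denominator, as for scarring. This SAP amendment follows database lock, so label the table post hoc.
3. Keep Table 14.2.15.3.2 as planned, with a footnote that milia on a healed wound count as 'Not Improved' and that the result is not to be read as wound worsening. Put the same footnote on the recessive dystrophic EB table.
4. Add the missing granulation tissue table, or record in SAP 5.2 that the endpoint was dropped.

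The coding of inflammation, blistering, erythema and exudate can stay.

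The cost is a few lines of SAP text and two descriptive tables from data already collected. The downside is that closed wounds are a post-randomisation subset, about 75 × 0.60 = 45 v 75 × 0.35 = 26, so the arms may differ in who closes. The comparison is also imprecise: with milia at 40% in both arms, the 95% CI half-width for the difference is 1.96 × √(0.24/45 + 0.24/26) = 0.237, about 24 percentage points. It should carry no test.
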